8.5.2 Final Model Construction

Based on the results of the above assessments, the final base model will be judged and finalized.

8.5.3 Covariate Model Construction

If applicable, the following covariates will be evaluated for their potential significant impact on the PK. Age, race and ethnicity, gender, all current medical conditions, all medical history relevant to iron deficiency diagnosis regardless of onset, all clinically significant medical history from the past five years including all malignancies, sterilisations, hospitalisations and surgeries, the method of contraception for female subjects of childbearing potential and body weight.

8.5.4 Concentration Prediction and Parameter Derivation

The serum iron, plasma maltol, plasma maltol glucuronide concentration, and TSAT versus time profile on Days 1 and 10 will be predicted for each subject using the individual PK parameters estimates from the final model.

Standard non-compartmental methods (NCA) will be used for the PK parameter calculations based on the predicted concentrations. The Linear Up Log Down method (equivalent to the Linear Up/Log Down option in WinNonlin® Professional) will be used in the computation of AUC.

Maltol and maltol glucuronide:

The following parameters for Day 1 will be derived for each Ferric Maltol dose based on the predicted maltol and maltol glucuronide concentrations, if applicable:

Table 4 Parameters for Maltol and Maltol Glucuronide on Day 1

Parameters	Description
C_{\max}	Maximum plasma concentration directly from data
T_{\max}	Time to reach maximum concentration directly from data
λ_z	Apparent first-order terminal elimination rate constant
$t_{1/2}$	Terminal elimination half-life, calculated as $\ln(2)/\lambda_z$
AUC_{0-6h}	Area under the plasma concentration versus time curve from time zero to 6hr.
$AUC_{0-\infty}$	Area under the plasma concentration versus time curve from time zero extrapolated to infinity time
CL/F	Apparent clearance calculated as Dose/ $AUC_{0-\infty}$
V_z/F	Apparent volume of distribution (as Dose/ $[\lambda_z * AUC_{0-\infty}]$)

The following parameters for Day 10 will be derived for each subject based on the predicted maltol and maltol glucuronide concentrations, if applicable:

Table 5 Parameters for Maltol and Maltol Glucuronide on Day 10

Parameters	Description
Tau	The dosing interval for steady-state data tau=12
C_{max}	Maximum concentration between dose time and dose time + Tau. If not unique, then the first maximum is used.
C_{trough}	Minimum concentration between dose time and dose time + Tau
T_{max}	Time to reach C_{max} during a dosing interval
AUC_{0-6h}	Area under the plasma concentration versus time curve from time zero to 6hr.
AUC_{0-tau}	Area under the plasma concentration versus time curve from time zero to Tau
$C_{ave(0-6h)}$	Average Steady State Plasma Concentration from 0-6h, calculated as AUC_{0-6h} divided by 6
CL_{ss}/F	Apparent clearance calculated as Dose/ AUC_{0-tau}
R_{Cmax}	Accumulation ratio based on maximum concentrations after first dose and last dose, calculated as $C_{maxDay10}/C_{maxDay1}$
$R_{AUC0-6h}$	Accumulation ratio based on AUC_{0-6} after first dose and last dose, calculated as $AUC_{0-6(Day10)}/AUC_{0-6(Day1)}$

Pharmacokinetic parameters of maltol and maltol glucuronide will be listed by dose group for each individual subject and summarized by dose group using the following descriptive statistics: n (the number of subjects), arithmetic mean, SD (standard deviation), geometric mean, geometric CV (coefficient of variation), median, minimum and maximum.

Plasma concentration-time courses of maltol/maltol glucuronide on Day 1 and Day 10, including C_{trough} , will be tabulated and graphically displayed per subject and summary statistics will be provided for each dose group for a specific timepoint/day. Plots of mean and geometric mean and plots with combined individual time courses will be provided by dose group.

Actual and/or dose-normalized pharmacokinetic parameters of C_{max} and AUCs will be graphically displayed for maltol and maltol-glucuronide as function of the dose, to explore dose-proportionality.

Serum iron and TSAT:

The following parameters for serum iron and TSAT on Day 1 will be derived for each subject based on the uncorrected and baseline-corrected predicted serum iron concentrations and TSAT, if applicable:

Table 6 Parameters for Serum Iron and TSAT on Day 1

Parameters	Description
C_{\max}	Maximum plasma concentration directly from data
C_{trough}	Pre-dose plasma concentration
Change from C_{trough} to C_{\max}	$C_{\max} - C_{\text{trough}}$
T_{\max}	Time to reach C_{\max}
λ_z	Apparent first-order terminal elimination rate constant
AUC_{0-6h}	Area under the plasma concentration versus time curve from time zero to 6 h using the pre-dose adjusted concentration data
$AUC_{0-\infty}$	Area under the plasma concentration versus time curve from time zero extrapolated to infinity time using the pre-dose adjusted concentration data
CL/F	Apparent clearance calculated as Dose/ $AUC_{0-\infty}$
V_z/F	Apparent volume of distribution (as Dose/ $[\lambda_z * AUC_{0-\infty}]$)

The following parameter for serum iron and TSAT on Day 10 will be derived for each subject based on the uncorrected and baseline-corrected predicted serum iron concentrations and TSAT, if applicable:

Table 7 Parameters for Serum Iron and TSAT on Day 10

Parameters	Description
Tau	The dosing interval for steady-state data tau=12
C_{\max}	Maximum concentration between dose time and dose time + Tau. If not unique, then the first maximum is used.
C_{trough}	Minimum concentration between dose time and dose time + Tau
Change from C_{trough} to C_{\max}	$C_{\max} - C_{\text{trough}}$
AUC_{0-6h}	Area under the plasma concentration versus time curve from time zero to 6 h using pre-dose adjusted concentration data
$AUC_{0-\tau}$	Area under the plasma concentration versus time curve from time zero to Tau
$C_{\text{ave}(0-6h)}$	Average Steady State Plasma Concentration from 0-6h, calculated as AUC_{0-6h} divided by 6
CL/F	Apparent clearance calculated as Dose/ $AUC_{0-\tau}$
$R_{C_{\max}}$	Accumulation ratio based on maximum concentrations after first dose and last dose, calculated as $C_{\max\text{Day10}}/C_{\max\text{Day1}}$
$R_{AUC0-6h}$	Accumulation ratio based on AUC_{0-6} after first dose and last dose, calculated as $AUC_{0-6(\text{Day10})}/AUC_{0-6(\text{Day1})}$

Pharmacokinetic parameters of serum iron and TSAT will be listed by dose group for each individual subject and summarized by dose group using the following descriptive statistics: n (the number of subjects), arithmetic mean, SD (standard deviation), geometric mean, geometric CV (coefficient of variation), median, minimum and maximum.

Concentration-time courses of serum iron and TSAT on Day 1 and 10, including C_{trough} on Day 1 and 10 will be tabulated and graphically displayed per subject and summary statistics will be provided for each dose group and visit/timepoint. Plots of mean and geometric mean and plots with combined individual time courses will be provided by dose group.

Actual and/or dose-normalized pharmacokinetic parameters of C_{\max} and AUCs will be graphically displayed for serum iron and TSAT as function of the dose, to explore dose-proportionality.

If the PPK model is not feasible for TSAT and PPD model is used for TSAT, the following parameters for TSAT on Days 1 and 10 will be derived for each subject based on the predicted TSAT, if applicable:

Table 8 Parameters for TSAT on Days 1 and 10

Parameters	Description
Baseline	Baseline response value before dosing
R _{max}	Maximum response value
R _{min}	Minimum response value
T _{max}	Time to reach R _{max}
T _{min}	Time to reach R _{min}
AUC _{0-6h}	Area under the effect versus time curve from time zero to 6 h
AUC _{0-24h}	Area under the effect versus time curve from time zero to 24 h
AUC_Above_B	Area under the response curve that is above the baseline
AUC_Below_B	Area that is below the baseline and above the response curve
AUC_Net_B	= AUC_Above_B - AUC_Below_B
Time_Above_B	Total time that response >= Baseline
Time_Below_B	Total time that response < Baseline

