6.3 PRIMARY ENDPOINTS

1. Population PK analysis of maltol and maltol glucuronide in plasma from PK samples collected on Day 1 (after first morning dose) and Day 10 (after last morning dose). Parameters to be derived and reported for each Ferric Maltol dose will be:

C_{max} , $C_{ave(0-6h)}$, $AUC_{(0-6h)}$, $AUC_{(0-inf)}$ on Day 1 and Day 10, and ratios of Day 10/Day 1 for these parameters.

T_{max} , half-life ($t_{1/2}$).

Apparent systemic clearance (CL/F), apparent volume of distribution (V/F).

Descriptive statistics for plasma concentrations of maltol and maltol glucuronide by time of collection on Day 1 and Day 10 will also be presented, including C_{trough} .

2. Descriptive and population PK analysis of serum iron and TSAT from PK samples collected on Day 1 and Day 10. Parameters to be derived and reported for each Ferric Maltol dose will be:

Change from pre-dose (C_{trough}) to maximum post-dose (C_{max}) value for serum iron and TSAT; $C_{ave(0-6h)}$.

Pre-dose adjusted Incremental $AUC_{(0-6h)}$ on Day 1 and Day 10 from a population PK analysis approach, and percentage change from Day 1 to Day 10.

Apparent systemic clearance (CL/F), apparent volume of distribution (V/F).

Descriptive statistics for serum iron and TSAT by time of collection on Day 1 and Day 10 will also be presented.

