8.5.1 Basic Model Construction

The maltol and maltol glucuronide concentrations will be analysed simultaneously by means of fitting the compartment models to observed concentration data using a population PK (PPK) approach.

Likewise, the serum iron and TSAT concentrations will be analysed. If the PPK modelling for TSAT is not feasible, population PD (PPD) approach may be performed.

Population PK models will be built using a nonlinear mixed effects modelling technique with NONMEM® software. It is planned that the first order conditional estimation with interaction (FOCEI) method will be used for model development. If this is not feasible (i.e. the model will fail to converge), the first order conditional estimation (FOCE) and the first order (FO) method will be used instead.

Different models will be attempted to fit the PK concentration-time data. The models will include, but are not limited to, one-compartment linear model, one-compartment linear model with first order absorption, two-compartment linear mammillary model, two-compartment linear mammillary model with first order absorption, three-compartment linear model, and three-compartment linear model with first order absorption, linear compartment model with zero order absorption or saturable absorption. Furthermore, a nonlinear compartment model may also be tested, if possible.

For each individual model, model stability will be assessed with the following:

- Model parameter estimates not close to a boundary;
- Shrinkage for interindividual variability terms (ETA) and residual unknown variability (EPS) < 30%;
- Condition number (ratio of the largest to the smallest eigenvalues) < 1000; and
- Correlation less than 0.90 between any two parameter estimates.

For the final PPK model, diagnostic plots will be presented and assessed.

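### The primary Day 10/Day 1 ratios for maltol and maltol glucuronide come from model-predicted curves with no planned study-day term, so they will read about 1.00 and cannot show a fall in Day 10 exposure

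*SAP*

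**What the plan says.** Protocol 6.3 and SAP 3.1 make the Day 10/Day 1 ratios part of primary endpoint 1. The protocol asks for Cmax, Cave(0-6h), AUC(0-6h) and AUC(0-inf) "on Day 1 and Day 10, and ratios of Day 10/Day 1 for these parameters".

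SAP 8.5.4 sets the derivation. Each concentration-time "profile on Days 1 and 10 will be predicted for each subject using the individual PK parameters estimates from the final model", and the parameters are calculated by NCA on those predictions. Table 5 describes R_Cmax as "Accumulation ratio based on maximum concentrations after first dose and last dose, calculated as" the Day 10 value over the Day 1 value, and defines R_AUC0-6h in the same way. Table 4 describes Day 1 Cmax as "Maximum plasma concentration directly from data", although the sentence introducing that table bases its parameters on predicted concentrations.

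The model is described in SAP 8.5.1 to 8.5.3:

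- The two analytes are fitted jointly: "The maltol and maltol glucuronide concentrations will be analysed simultaneously by means of fitting the compartment models to observed concentration data".
- The structural list is open: "The models will include, but are not limited to, one-compartment linear model".
- The random terms named are ETA (between subjects) and EPS (residual).
- The covariate list starts with "Age, race and ethnicity, gender, all current medical conditions, all medical history relevant to iron deficiency diagnosis regardless of onset" and continues with other history, contraception and body weight. Weight is measured only at Screening.

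Study day does not appear as a covariate, a random effect or a basis for separate fits. SAP 8.4 summarises and plots observed concentrations by dose group and visit, but forms no Day 10/Day 1 ratio from them.

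**The concern.** If each subject has one set of parameters for both days, the Day 10 curve differs from the Day 1 curve only by what remains of the earlier doses. That gives a correct accumulation ratio under linear, time-constant pharmacokinetics. It does not estimate how Day 10 exposure compares with Day 1 exposure, because the model has already assumed that clearance and bioavailability are unchanged.

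A real fall by Day 10 in absorption of maltol, or in formation of glucuronide, would therefore be tabulated as a ratio of about 1.00. That value would appear to confirm the adult finding in Protocol 5.4 of no accumulation over a week of dosing, without having tested it. The results of this study are to inform dose selection for the paediatric Phase 3 study.

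**Working it through.** The documents state no ratio to reproduce. The check is what the planned derivation returns.

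**Inputs.** Adult half-lives are 0.8 h (maltol) and 1.1 h (glucuronide), with median Tmax 1.0 h for both and inter-subject variability in AUC of about 27% (Protocol 5.4). The dosing interval is 12 h (SAP Table 5). There are 2 × 9 + 1 = 19 doses (SAP 4.4.7). Sampling windows are from SAP Table 3.

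**Carry-over factor.** R = 1/(1 − exp(−k × 12)), with k = ln 2 / t½.

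- Maltol: k = 0.866 per h, exp(−10.40) = 0.00003, R = 1.00003.
- Glucuronide: k = 0.630 per h, exp(−7.56) = 0.0005, R = 1.0005.

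**Full profile.** For one compartment with first-order absorption, C(t) is proportional to [ka/(ka − k)] × (exp(−kt) − exp(−ka·t)). Solving ln(ka/k)/(ka − k) = 1.0 h gives ka = 1.147 and 1.492 per h. The Day 10 curve is the sum of C(t + 12j) for j = 0 to 18.

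| Half-life | Carry-over factor | R_AUC0-6h |
|---|---|---|
| 0.8 h (maltol) | 1.00003 | 1.0001 |
| 1.1 h (glucuronide) | 1.0005 | 1.0009 |
| 1.6 h (0.8 h doubled) | 1.0056 | 1.007 |
| 2.2 h (1.1 h doubled) | 1.023 | 1.028 |
| 4 h | 1.143 | 1.157 (R_Cmax 1.152) |

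Every added term is non-negative, so the Day 10 curve is never below the Day 1 curve and the ratio is never below 1, whatever the half-life. Numerical examples with saturable absorption or saturable elimination gave 1.000 to 1.03.

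**Simulation of the planned design.** Both analytes, 36 subjects, Table 3 windows, 100 replicates per case. Assumptions: 27% between-subject variability on CL and V, 15% inter-occasion variability on F, residual error 20% or 40%, no LLOQ, first-order linearised likelihood, starts at the true values, post-dose samples only.

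| True ratio, maltol / glucuronide | Mean planned R_AUC0-6h | Mean with separate day effects | Median OFV drop from day effects (20% / 40% error) |
|---|---|---|---|
| 0.5 / 0.5 | 1.001–1.002 | 0.50 / 0.50 | 270 / 141 |
| 0.7 / 0.7 | 1.001–1.002 | 0.70 / 0.70 | 110 / 49 |
| 1.0 / 0.5 | 1.001–1.002 | 0.99–1.00 / 0.50 | 136 / 71 |

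With true ratios of 0.5 or 0.7 for both analytes, the largest single fit without a day term was 1.010. With separate day effects the SE of the log ratio was 0.04 to 0.08, a 95% CI of about ×/÷ exp(1.96 × 0.04) = 1.08 to exp(1.96 × 0.08) = 1.17. In the 1.0 / 0.5 case, a single F effect shared by both analytes gave 0.71 for each, so the effect has to be separate by analyte.

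A second simulation used one analyte at a time, a penalised individual fit, 25% residual error and 10 replicates per case. It reported 1.001 to 1.003 without a day term. With one, it recovered 0.71 to 0.72 (true 0.70) and 0.50 to 0.51 (true 0.50). The observed paired geometric mean ratios in the same data were 0.70 to 0.73 and 0.50 to 0.51. The data carry the signal and the planned derivation removes it.

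**Table 4 wording.** If Day 1 Cmax were the larger of the two observed samples, R_Cmax with no true change would be about 1.04 (schedule groups 1 and 2), 1.09 to 1.10 (group 3) and 1.68 to 1.78 (group 4), with samples at mid-window. That reading does not give a day effect either.

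**The case against.** **A day term is allowed.** The model list is open, a nonlinear model may be tested, and SAP 4.2.2 asks for parameters on each day. A model with time-dependent clearance could give a ratio below 1. This is true, but no time-varying parameter is named, and a primary endpoint should not depend on an analyst adding one unprompted.

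**The SAP already calls these accumulation ratios.** It does, and the label is accurate. But the endpoint in Protocol 6.3 is the Day 10/Day 1 ratio of exposure, and nothing else in the SAP supplies it.

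**A large fall would be seen.** This stands in part. The SAP says: "For the final PPK model, diagnostic plots will be presented and assessed". In the simulation the fitted residual SD rose from 0.24 to 0.47 (20% error, true ratio 0.5), and observed values are summarised by visit. Falls milder than 0.7 were not simulated. Even where a fall is noticed, no ratio or interval is planned outside the predicted curves, so the tabulated primary result would still be about 1.00.

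**Rises.** The result is not claimed for increases. In a one-analyte simulation of a doubling, single fits without a day term reached 1.42.

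**Relevance.** The adult study showed no accumulation and no clear link between iron uptake and maltol exposure, so there is no specific reason to expect a fall. This limits the likely consequence but does not make the ratio informative.

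**Conclusion.** The concern holds. Followed as written, the SAP reports a Day 10/Day 1 ratio of about 1.00 for maltol and glucuronide even if true exposure has fallen by 30% or 50%. The value of about 1.00 rests on adult half-lives; at 4 h it would be about 1.15. That the ratio cannot fall below 1 does not depend on the half-life. It follows directly for the linear time-constant models listed, and held in the saturable examples tried. The simulation sizes rest on the stated variability and error assumptions.

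This should be fixed before analysis, but it does not invalidate the study: the samples needed are already planned and the observed data offer a partial safeguard. For serum iron and TSAT the point is narrower. No day effect is planned there either, and Table 7 does not say which pre-dose value is subtracted on Day 10.

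**What to change.** 1. In SAP 8.5.1 and 8.5.3, prespecify study day (Day 10 versus Day 1) as an effect on exposure, estimated separately for each analyte, for example on relative F for maltol and on formation or clearance for glucuronide. Add inter-occasion variability where it can be estimated.
2. Report the Day 10/Day 1 ratio with a 95% CI from that model. Keep the accumulation label for the ratio of curves predicted without a day effect, and do not present it as the endpoint.
3. As support, report the observed within-subject ratio in matched windows (geometric mean, 95% CI, overall and by dose group). Each subject has the same schedule on both days.
4. For that observed ratio, treat BQL values as censored, or add a sensitivity analysis, and state the number of BQL pairs. The zero rule in SAP 8.3 cannot be used in a geometric mean, and dropping pairs biases it. The documents give no LLOQ, so 1 to 10 ng/mL was assumed for maltol at 7.8 mg with a true ratio of 0.5. At 5 ng/mL, dropping pairs gave 0.53 to 0.58 and a censored analysis 0.50. At 10 ng/mL the figures were 0.65 to 0.72 and 0.47 to 0.48. At 1 ng/mL both gave 0.50 to 0.51.
5. State in Table 4 that Cmax and Tmax come from predicted values. For serum iron and TSAT, state the Day 10 pre-dose value used and whether a day effect is fitted.

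The cost is SAP wording, one or two parameters per analyte and one table. Inter-occasion variability may not be estimable, and the added terms must meet the SAP's shrinkage and correlation limits with two post-dose samples per day. Observed ratios by dose group will be imprecise: with 12 subjects the 95% CI is about ×/÷ 1.2 to 1.4, and about ×/÷ 2.0 for maltol at 7.8 mg if exposure halves and the LLOQ is 10 ng/mL.

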The pharmacokinetics (PK) and iron uptake of 30mg Ferric Maltol BID were confirmed in a cohort of 15 IBD patients participating in the open-label phase of studies ST10-01-301 and ST10-01-302 (Shield TX, data on file for sub-study ST10-01-102). Plasma concentrations of maltol above the limit of assay detection were transiently observed between 15min and 4h after dosing (mean Cmax 67.3ng/mL; median Tmax 1.0h; mean AUC 136h*ng/mL; mean t1/2term 0.8h). However, consistent with earlier studies of Ferric Maltol, maltol glucuronide predominated in plasma (mean Cmax 4677ng/mL; median Tmax 1.0h; mean AUC 9651h*ng/mL and mean t1/2term 1.1h). Maximal change in serum iron and TSAT was observed 2h after dosing, however in many subjects it was apparent from the TSAT rises that iron uptake was occurring from 30 minutes. The inter-subject variability for AUC of both maltol and maltol-glucuronide in this cohort was low (approximately 27%).

Another open-label, randomised Phase 1 study evaluated the pharmacokinetics of Ferric Maltol and its effect on iron indices in patients with iron deficiency (with or without anaemia). Twenty-four subjects received Ferric Maltol 30, 60, or 90 mg BID over an 8-day period. Pharmacokinetics and iron uptake were assessed on Days 1 and 8. Ferric maltol showed predictable pharmacokinetics, no accumulation over 7 days, and improvements in iron uptake across the dose range 30–90 mg BID (Bokemeyer, 2016). Maximum serum concentrations of total iron were reached between 2 and 3 hours' post-dose. Initially a slight decline in serum total iron concentrations was observed, followed by an increase to on average 32.3, 49.1 and 48.7 μ mol/L on Day 1 for the 30 mg, 60 mg and 90 mg BID dose groups, respectively. Serum total iron concentrations gradually declined after reaching Tmax and mean serum concentrations were 11.8, 33.0 and 24.3 μ mol/L above baseline at 6 hours' post-dose on Day 1 for the 30 mg, 60 mg and 90 mg BID dose groups, respectively. Comparable serum concentrations were measured on Day 8. Plots comparing total iron and the exposure to maltol and maltol glucuronide showed no clear relationship.

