3 STUDY ENDPOINTS

3.1 Primary Endpoints

The primary endpoints for the study are pharmacokinetic parameters.

1. Population PK analysis of maltol and maltol glucuronide in plasma from PK samples collected on Day 1 (after first morning dose) and Day 10 (after last morning dose). Parameters to be derived and reported for each Ferric Maltol dose are:
 - C_{max} , $C_{ave(0-6h)}$, $AUC_{(0-6h)}$, and $AUC_{(0-Inf)}$ on Day 1 and Day 10 and ratios of Day 10/Day 1 for these parameters;
 - T_{max} ;
 - Half-life ($t_{1/2}$);
 - Apparent systemic clearance (CL/F); and
 - Apparent volume of distribution (V/F).

Plasma concentrations, including C_{trough} of maltol and maltol glucuronide by time of collection on Day 1 and Day 10 will also be presented.

2. Descriptive and population PK analysis of serum iron and TSAT from PK samples collected on Day 1 and Day 10. Parameters to be derived and reported for each Ferric Maltol dose are:
 - Change from pre-dose (C_{trough}) to maximum post-dose (C_{max}) value for serum iron and TSAT; $C_{ave(0-6h)}$;
 - Pre-dose adjusted Incremental $AUC_{(0-6h)}$ on Day 1 and Day 10 from a population PK analysis approach, and percent change from Day 1 to Day 10; and
 - Apparent systemic clearance (CL/F), apparent volume of distribution (V/F).

Serum iron and TSAT by time of collection on Day 1 and Day 10 will also be presented.

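### SAP 8.5.4 re-derives Day 1 CL/F, V/F and half-life by NCA on model-predicted curves instead of reporting the model's own estimates; the added error depends on settings the SAP does not state

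*SAP*

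**What the plan says.** SAP 3.1 lists among the primary parameters "Apparent systemic clearance (CL/F), apparent volume of distribution (V/F"), and half-life for maltol and maltol glucuronide. Protocol 12.2.1 places the maltol and glucuronide values under population PK analysis. It names non-compartmental methods only for the pre-dose adjusted AUC(0-6h) of serum iron and TSAT.

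In SAP 8.5.4 the profiles on Days 1 and 10 "will be predicted for each subject using the individual PK parameters estimates from the final model". Then: "Standard non-compartmental methods (NCA) will be used for the PK parameter calculations based on the predicted concentrations". For Day 1 (Tables 4 and 6) the rows are:

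- lambda_z: "Apparent first-order terminal elimination rate constant".
- CL/F: "Apparent clearance calculated as Dose" over AUC(0-inf).
- Vz/F: Dose/(lambda_z x AUC(0-inf)).
- Half-life, Table 4 only: "Terminal elimination half-life, calculated as" ln(2)/lambda_z.

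Table 6 is to be produced from uncorrected as well as baseline-corrected curves. Its AUC rows specify pre-dose adjusted data; its lambda_z row does not. For Day 10, Tables 5 and 7 set "The dosing interval for steady-state data tau=12", derive clearance from AUC(0-tau), and have no lambda_z, V/F or half-life row. SAP 4.2.2 nevertheless promises half-life and V/F for all four analytes on both days.

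The prediction grid, the Day 1 horizon and the rule for choosing lambda_z points are not given. SAP 14 declares no planned changes from the protocol.

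**The concern.** A population model with linear elimination already estimates CL/F and V/F, with standard errors and between-child variance, and half-life follows from them. Generating a curve from those estimates and re-estimating them from the curve brings in no new information. It does bring in two numerical errors. If absorption is not finished at the end of the curve, lambda_z is too small, so half-life and V/F are too large. If the grid is coarse, the trapezoids misstate AUC and hence CL/F. In a multi-compartment model, Vz/F is also a different quantity from the model's volume terms.

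For serum iron and TSAT there is a further problem: a terminal slope taken from a curve that still contains the endogenous baseline is not an elimination rate.

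These are primary parameters in a study meant to inform Phase 3 paediatric dose selection. Part of what is reported could reflect the programmer's settings rather than the children.

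**Working it through.** The plan gives no figure to reproduce (SAP 13 states that no formal sample size calculation was done). I applied NCA to noise-free curves with known CL and V, so any departure from 1.00 comes from the NCA step.

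**1. Model and formulas.** One compartment, first-order absorption: C(t) = (Dose/V) x ka/(ka - k) x (e^(-kt) - e^(-ka t)), with CL = kV. AUC is linear-up/log-down as in SAP 8.5.4, plus C_last/lambda_z. Assumed: lambda_z from the last three points. Ratios are NCA/model: half-life = k/lambda_z; CL/F = true AUC/NCA AUC; V/F = the product of the two.

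**2. Maltol.** Protocol 5.4 gives adult Tmax 1.0 h and half-life 0.8 h. So k = ln2/0.8 = 0.866, and ln(ka/k)/(ka - k) = 1.0 gives ka = 1.147.

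| Horizon, grid | Half-life | CL/F | V/F |
|---|---|---|---|
| 6 h, 1 h | 1.122 | 1.105 | 1.240 |
| 6 h, 0.5 h | 1.097 | 1.025 | 1.124 |
| 6 h, 0.05 h | 1.081 | 1.000 | 1.081 |
| 12 h, 1 h | 1.016 | 1.106 | 1.124 |
| 12 h, 0.5 h | 1.014 | 1.025 | 1.039 |
| 12 h, 0.05 h | 1.012 | 1.000 | 1.012 |
| 24 h, 1 h | 1.001 | 1.106 | 1.107 |
| 24 h, 0.05 h | 1.000 | 1.000 | 1.001 |

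The horizon drives the half-life error and the grid drives the CL/F error, so a longer horizon does not cure a coarse grid. For glucuronide (Tmax 1.0 h, half-life 1.1 h; k = 0.630, ka = 1.492) V/F is +2 to +12% on coarse grids at 6-12 h and +1% or less on dense ones.

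**3. Serum iron, baseline-corrected.** Protocol 5.4, 30 mg, Day 1: total peak 32.3 umol/L, 11.8 above baseline at 6 h; "Maximum serum concentrations of total iron were reached between 2 and 3" hours. The pre-dose level B is not given; I assume 8, 10 and 12 umol/L. The required C6/Cmax = 11.8/(32.3 - B) is 11.8/24.3 = 0.486, 11.8/22.3 = 0.529 and 11.8/20.3 = 0.581. I tried Tmax 2, 2.5 and 3 h with a lag of 0 or 0.5 h. The lowest ratio this model can reach is 0.592 at Tmax 2.5 h without lag, 0.736 at Tmax 3 h without lag and 0.663 with it, so those cases cannot be fitted. The remaining fits, on grids of 0.05 to 1 h, give:

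- 6 h: V/F about 0 to +43%, CL/F x0.92 to 1.00.
- 12 h: V/F -1 to +8%, CL/F within about 2%.

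The upper end is B = 8, Tmax 2.5 h, lag 0.5 h (ka 0.59, k 0.416). A finer search over B, Tmax and lag reaches +69% at 6 h and +24% at 12 h, only where ka is within about 5% of k.

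**4. Serum iron, lambda_z from the uncorrected curve.** Once absorption is over, the log-slope of B + C is k x C/(B + C), so half-life is multiplied by (B + C)/C. At 6 h, C = 11.8, giving 19.8/11.8 = 1.68, 21.8/11.8 = 1.85 and 23.8/11.8 = 2.02 for B = 8, 10, 12. At 12 h, for the B = 10, Tmax 2 h, lag 0.5 h fit (k = 0.190): C = 11.8 x e^(-0.190 x 6) = 3.77, and 13.77/3.77 = 3.65. Over all the step 3 fits, this lambda_z with the pre-dose adjusted AUC gives V/F x1.6 to 2.2 at 6 h and x3.0 to 7.3 at 12 h. If the same slope is also used to extrapolate the AUC, the factors are x1.3 to 1.9 and x2.3 to 6.3, and CL/F falls to x0.68 to 0.90.

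**5. Limit of the model.** Adult maltol Cmax/AUC is 67.3/136 = 0.495; the one-compartment curve gives k x e^(-k x Tmax) = 0.364. The sizes are indicative.

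**The case against.** The strongest reply is that the curves are predictions, so nothing ties them to the 6 h sampling limit. Day 10 uses 12 h, Table 8 (the fallback for TSAT) needs 24 h, and a single dose can be simulated to any length. On a dense, long, baseline-corrected curve the error is negligible unless absorption is rate-limiting. That stands: the error is not built into the method. But the SAP does not require such a curve.

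Second, nothing says the model's estimates will go unreported; the stability checks in SAP 8.5.1 are applied to them. That also stands. What can be said is that no table lists them, not that they are to be withheld.

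Third, NCA gives one definition across candidate models. SAP 8.5.1 allows nonlinear ones, for which a single clearance or half-life may not exist, and the adult data are quoted as terminal half-lives. This justifies an exception in the fix, not the present default.

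A reader might go further in three ways that the documents do not support:

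- That CL/F is inflated generally. On dense grids it is unchanged for maltol and glucuronide; for corrected iron it is somewhat low at 6 h.
- That serum iron is always the worst affected. On corrected curves its range overlaps that of maltol; only an uncorrected slope sets it apart.
- That both days are affected. Tables 5 and 7 contain no lambda_z-based quantity.

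**Conclusion.** The point holds as a choice of method for Day 1. SAP 8.5.4 takes primary parameters from a second calculation on the model's own curves and leaves open the settings that decide its error. For maltol V/F the range runs from about +24% on a coarse 6 h curve to about 1% or less on a dense 12 to 24 h curve. CL/F is materially affected only by a coarse grid (about +10% at 1 h) or, for iron, biased somewhat low on a 6 h curve. For comparison, Protocol 5.4 puts adult between-subject variability in maltol and glucuronide AUC at approximately 27%.

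The firmest part concerns Table 6: an uncorrected lambda_z with the adjusted AUC would inflate iron V/F about two-fold at 6 h and three-fold or more at 12 h, somewhat less if that slope also extrapolates the AUC. TSAT has the same table and the same gap; I did not size it.

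These sizes assume adult kinetics, one compartment, three-point lambda_z, and an iron baseline of 8-12 umol/L. If absorption were slower than elimination (for example ka 0.3/h, k 0.6/h), lambda_z would return the absorption rate and half-life and V/F would be x2.0 even on a dense 48 h curve.

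**What to change.** In SAP 8.5.4:

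1. Where the final model has linear elimination, report CL/F, V/F and half-life from it: typical values with standard errors, between-child variance and individual estimates. If it is multi-compartment, label V/F by compartment.
2. Keep NCA on predicted curves for Cmax, Tmax, AUC(0-6h) and Cave(0-6h), on a stated fine grid (for example 0.05 h).
3. If lambda_z-based rows are kept, for a nonlinear model or for comparison with adult terminal half-life, run them on a dense single-dose curve with a stated long horizon (for example 24 h or more) and a stated point-selection rule. AUC(0-inf) by NCA belongs with these rows. For serum iron and TSAT use baseline-corrected curves only.
4. Reconcile SAP 4.2.2 with Tables 4 to 7 on which analytes and days have half-life and V/F. Record in SAP 14 any use of NCA beyond what Protocol 12.2.1 names.

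The cost is SAP wording before database lock. No extra data are needed, and the model values are standard NONMEM output.
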